2 LIST OF ABBREVIATIONS

Abbreviation	Definition		
ADS	Analytical dataset specification		
ATC	Anatomical Therapeutic Chemical		
BIPS	Leibniz Institute for Prevention Research and Epidemiology		
CépiDc	Centre d'épidémiologie sur les causes médicales de Décès		
	(epidemiological Centre on medical causes of Death)		
CESREES	Comité éthique et scientifique pour les recherches, les études et les		
	évaluations dans le domaine de la santé (Ethical and Scientific		
	Committee for Research, Studies and Evaluations in the Health Field)		
CMI	Concomitant medication(s) of interest		
CNIL	Commission Nationale de l'Informatique et des Libertés (National		
	Commission on Informatics and Liberty)		
CNS	Central nervous system		
DUS	Drug utilisation study		
EMA	European Medicines Agency		
ERT	Enzyme replacement therapy		
EU	European Union		
GD	Gaucher disease		
GD1	Gaucher disease type 1		
GePaRD	German Pharmacoepidemiological Research Database		
GP	General practitioner		
НСР	Health care provider		
ICD-10	International Classification of Diseases and related health problems, 10th		
	edition		
IEC	Independent Ethics Committee		
LSD	Lysosomal storage disease		
NHS	National Health Service		
NPR	National Prescription Registry		
PRAC	Pharmacovigilance Risk Assessment Committee		
SAP	Statistical analysis plan		
SmPC	Summary of products characteristic		
SNDS	Système National des Données de Santé (National Health Data System)		
SRT	Substrate reduction therapy		

3 RESPONSIBLE PARTIES

Note that formal participation of each data source to the study will be dependent on Ethics Committee approval. Also, these data sources accepted to participate but not all research agreements have been signed yet.

4 ABSTRACT

Protocol Title:	Error! Reference source not found.	
Protocol Number:	Error! Reference source not found.	
Protocol Version:	Error! Reference source not found.	
Protocol Date:	Error! Reference source not found.	
Author (of version 3.0):	[name] on behalf of Sanofi	
	Medical Writing Services Parexel International	
Sponsor:	Error! Reference source not found.	
Study Centres:	France, Denmark, Germany and Israel	
Rationale and Background:	Eliglustat (Cerdelga [®]) is an oral treatment indicated in Europe for the long-term treatment of adult patients with Gaucher Disease Type 1 (GD1) who are CYP2D6 poor metabolisers, intermediate metabolisers or extensive metabolisers. Eliglustat is metabolised primarily by the cytochrome P450 enzyme CYP2D6, and to a lesser extent by the cytochrome P450 enzyme CYP3A. The ability to metabolise drugs through the CYP2D6 pathway may vary between individuals, leading to intervariable plasma concentrations of eliglustat depending on the individual's CYP2D6 metaboliser phenotype. The concomitant use of drugs inhibiting the CYP2D6 and the CYP3A enzyme activity may lead to substantially elevated eliglustat plasma concentrations. On the other hand, concomitant use of strong CYP3A inducers, may decrease eliglustat plasma concentration of eliglustat may increase plasma concentrations of P-gp and CYP2D6 substrate substances.	
Research Question and Objectives:	The primary objective of this Drug Utilisation Study (DUS) is to estimate the dose and duration of eliglustat therapy as well as the proportion, therapeutic class, and duration of past and concomitant medication use in GD1 patients treated with eliglustat. The concomitant medications of interest (CMI) are strong and moderate CYP2D6 inhibitors, strong and moderate CYP3A inhibitors, strong CYP3A inducers, P-gp substrates and CYP2D6 substrates. Simultaneous use of strong or moderate CYP2D6 inhibitors with strong or moderate CYP3A inhibitors concomitantly with eliglustat will be explored, if feasible. The secondary objective of the DUS is to describe the healthcare service pattern (i.e., prescriber's specialty and types of patient visit) for the prescriptions of concomitant medications in patients treated with eliglustat.	
Study Design:	This is a drug utilisation study based on the follow-up of a cohort of GD1 patients treated with eliglustat. The study period will be from one year before the first prescription of eliglustat in each data source to the study end (i.e., data extraction date) planned on Q3 2024.	

Population:	Gaucher Disease Type 1 patients in France, Denmark, Germany and Israel who are prescribed eliglustat after approval of the drug in each country.		
Variables:	Data will be collected on dose and duration of eliglustat as well as on therapeutic class and duration of drugs used concomitantly with eliglustat that are susceptible to significantly interfere with eliglustat metabolism or whose plasma concentration might be altered by eliglustat intake. These drugs are strong and moderate CYP2D6 inhibitors, strong and moderate CYP3A inhibitors, strong CYP3A inducers, P-gp substrates and CYP2D6 substrates. Data will also be collected on the age, sex and death date of GD1 patients, as well as (whenever feasible) on prescriber's specialty and type of patient visit.		
Data Sources:	Use of secondary data from prescription databases running in the four selected countries. Of note, there is generally a time-lag (different for each selected country) between data collection and availability of complete set of data in prescription databases.		
Study Size:	All GD1 patients with an eliglustat prescription in the prescription databases will be included. A minimum number of 128 GD1 patients treated with eliglustat is expected.		
Data Analysis:	Descriptive analysis of eliglustat therapy in terms of duration and dose.		
	Descriptive analysis of the past medication use (one year prior to the exposure period) and concomitant medication use (i.e., during the exposure period) in terms of proportion, therapeutic class and duration.		
	Descriptive analysis of the healthcare service pattern (i.e., prescriber's specialty and types of patient visit) for the use of concomitant medications.		
Milestones:	A final report will be submitted at the latest in Q4 2024.		
	Milestone Planned Date		
	Start of data collection	Q3 2022	
	End of data collection	Q3 2024	
	Final report of study resultsQ4 2024		

5 AMENDMENTS AND UPDATES

This protocol was first written and submitted to Pharmacovigilance Risk Assessment Committee (PRAC) as version 1.0 in 2015. Due to the comments received from PRAC during the assessment procedure, the protocol was updated and finalised as version 2.0 and approved by PRAC. The protocol was then updated several times as internal draft versions (not finalised due to feasibility issues in relation to the access to the data in the different countries) and this last final version was updated in June 2023.

Version	Date	Section of study protocol	Amendment or update	Reason
3.0	23 June 2023	Throughout the protocol	Update	1. Information was updated due to the change of CRO.
				2. The protocol was transferred from the previous CRO's template to Parexel template.
				3. The sources of data were updated. Initially, this study was planned to be conducted in Belgium, Italy, Norway and Scotland. In 2020, Italy, Norway and Scotland were removed and replaced by France, Germany and Denmark. In 2021, Israel was also added to the DUS. Israel is considered as a European country since several agreements are in place between the European Union and Israel, including EMA agreements. In January 2023, Belgium was removed.
				4. Some missing information was added from the SAP, including endpoints.

Abbreviation: CRO = Contract Research Organisation; DUS = Drug Utilisation Study; EMA = European Medicines Agency; SAP = statistical analysis plan

6 MILESTONES

Milestone	Planned Date	
Registration in the EU PAS register	Q2 2020	
Start of data collection*	Q3 2022	
End of data collection*	Q3 2024	
Final report of study results	Q4 2024	

* Definition according to the GVP Module VIII - Post-authorisation safety studies (Rev 3) (accessible at: https://www.ema.europa.eu/en/documents/scientific-guideline/guideline-good-pharmacovigilance-practices-gvp-moduleviii-post-authorisation-safety-studies-rev-3_en.pdf)

Abbreviations: EU = European Union, GVP = Good pharmacovigilance practices, PAS = Post authorisation Study, Q = quarter

This Drug Utilisation Study (DUS) has been registered in the European Union (EU) PAS register in April 2020. Its registration number is EUPAS34611.

Data collection corresponds to the data extraction from each database and started in Q3 2022 (Germany). At this date, data spanning from one year before the first prescription of eliglustat to the date of last available data in each database will be extracted.

The end of data collection may be adjusted according to the date of last database update in each data source.

A final report will be submitted to the European Medicines Agency (EMA) at the latest in Q4 2024.

7 BACKGROUND AND RATIONALE

7.1 Background

Eliglustat, an oral substrate reduction therapy (SRT) for the treatment of Gaucher Disease Type 1 (GD1), is metabolised mainly by CYP2D6 and to a lesser extent by CYP3A4. Concomitant administration of substances affecting CYP2D6 or CYP3A4 activity may alter eliglustat plasma concentrations. Eliglustat is an inhibitor of P-gp and CYP2D6; concomitant administration of eliglustat with P-gp or CYP2D6 substrate substances may increase the plasma concentration of those substances. Therefore, it is important that the use of strong and moderate CYP2D6 inhibitors, strong and moderate CYP3A4 inhibitors, strong CYP3A4 inducers, P-gp substrates and CYP2D6 substrates as concomitant medications among patients treated with eliglustat be carefully monitored.

CYP2D6, a member of the cytochrome P450 mixed-function oxidase system, is one of the most important enzymes involved in the metabolism of xenobiotics in the body. CYP2D6 is responsible for the metabolism and elimination of approximately 25% of all clinically used drugs. For drugs that are metabolised by CYP2D6 (i.e., CYP2D6 substrates), certain individuals will eliminate these drugs very quickly (ultra-rapid metabolisers) while others will metabolise slowly (poor metabolisers). If a drug dose is metabolised too quickly, this may not achieve adequate plasma concentrations to achieve therapeutic effects. If a drug dose is metabolised too slowly, elevated plasma concentrations may occur, that potentially may lead to side effects. CYP2D6 metaboliser phenotype indicates the speed at which a drug is metabolised by CYP2D6. It can often be predicted, using genotyping, and is classified into four categories: poor (slow), intermediate, extensive, and ultra-rapid (fastest). Patients for whom no phenotype can be predicted based on genotyping are considered indeterminate metabolisers. Hence the patient's dose of a drug may have to be adjusted considering the patient's CYP2D6 metaboliser phenotype.

Certain drugs may function as inhibitors of CYP2D6 activity; decreased CYP2D6 enzyme activity could lead to increased plasma concentrations of CYP2D6 substrates. When administered concomitantly with CYP2D6 substrates, CYP2D6 inhibitor drugs might contribute to the occurrence of side effects. CYP2D6 inhibitor drugs can be classified as strong, moderate or weak inhibitors.

CYP3A is the most abundant cytochrome P450 enzyme in the body (mainly found in the liver and intestine) and is responsible for the metabolism of nearly 50% of therapeutic compounds. Certain drugs may function as inhibitors of CYP3A activity and can be classified as strong, moderate or weak inhibitors. Decreased CYP3A enzyme activity could lead to increased plasma concentrations of CYP3A substrates when administered concomitantly, and, in some cases, result in side effects.

Some drugs may function as inducers of CYP3A activity; increased CYP3A enzyme activity could lead to decreased plasma concentrations of CYP3A substrates.

Eliglustat is indicated in the EU for the long-term treatment of adult patients with GD1, who are CYP2D6 poor metabolisers, intermediate metabolisers or extensive metabolisers. Eliglustat is an inhibitor of P-gp and CYP2D6 in vitro; concomitant administration of eliglustat with P-gp or CYP2D6 substances may increase the plasma concentration of those substances. Eliglustat is contraindicated in patients who are CYP2D6 inhibitor concomitantly with a strong or moderate CYP3A inhibitor, and patients who are CYP2D6 poor metabolisers taking a strong CYP3A inhibitor. Use of eliglustat under these conditions results in substantially elevated eliglustat plasma concentrations.

Further details are available in the eliglustat (Cerdelga[®]) Summary of Product Characteristics (SmPC)¹.

7.2 Rationale for Study

It is clear from the pilot study conducted in Regione Lombardia in 2015 (Appendix 3 [Section 14.3]) that there is a significant prescription of concomitant medications among patients treated for GD in Europe, including CYP2D6 inhibitors and CYP3A inhibitors.

A study on the use of eliglustat and concomitant medications needs to provide a valid reflect of usage patterns prevailing in European countries. To this end, such study will be based on the collection and analysis of secondary data gathered in healthcare databases. These data provide exhaustive information on usage patterns of GD1 patients who are treated with eliglustat. However, a time-lag exists between the time of prescription and the time when this prescription appears in the database; this time-lag varies between data sources and can be several years. This time-lag needs to be considered for the conduct and reporting of a DUS on eliglustat. The pilot study conducted in Regione Lombardia in 2015 (Appendix 3 [Section 14.3]) showed the feasibility of using regional/national prescription databases for drug utilisation evaluation of concomitant medications.

Collection and assessment of concomitant drug use data cannot be determined in a short timeframe from one database or using a limited group of resources. A DUS of eliglustat should be undertaken in a series of prescription databases. Prescription databases must cover large populations to provide useful and reliable investigations of drug usage patterns in diseases as rare as GD. The DUS of eliglustat will be performed using existing databases including those of France, Denmark, Germany and Israel. This will provide a total population of approximately 100 million to identify GD patients from.

7.3 Risk Management Measures

The safety concerns relevant for eliglustat are primarily managed through routine risk minimisation activities: labelling recommendations and prescription status of the product, to be initiated and supervised by a physician knowledgeable in the management of GD.

Moreover, the following educational materials have been developed to reinforce knowledge and adherence of the prescribers and patients to the risks associated with the use of eliglustat, including:

- A guide for prescriber: targeted to specialists initiating and supervising eliglustat treatment including a checklist of steps to be performed prior to initiation of eliglustat.
- A patient alert card: targeted to Health Care Providers (HCP) who do not prescribe eliglustat regarding important drug-drug interactions with eliglustat and to ensure that the patient's risk for drug-drug interactions reach the relevant HCP. It is also targeted to patients who will be educated regarding self-medication, and to present the card to all other HCP at each visit.

Also, recommendations and precautions to be followed by healthcare professionals and patients for the safe and effective use of eliglustat have also been included in the summary of product characteristics and in the package leaflet of eliglustat.

This DUS will allow to assess the effectiveness of risk minimisation measures that have been put in place and also to improve them.

8 RESEARCH QUESTION AND OBJECTIVES

As part of pharmacovigilance activities of eliglustat risk management plan, this DUS will allow to assess the effectiveness of risk minimisation measures (EU labelling, guide for prescribers and patient alert card) regarding understanding and implementing avoidance of significant drug-drug interactions.

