8.1 Primary Objective

The primary objective of the DUS is to estimate the dose and duration of eliglustat therapy as well as the proportion, therapeutic class, and duration of past and concomitant medication use in patients treated with eliglustat. The concomitant medications of interest (CMI) are strong and moderate CYP2D6 inhibitors, strong and moderate CYP3A inhibitors, strong CYP3A inducers, P-gp substrates and CYP2D6 substrates (Appendix 1 in Section 14.1). Simultaneous use of strong or moderate CYP2D6 inhibitors with strong or moderate CYP3A inhibitors concomitantly with eliglustat will be explored, if feasible.

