9 RESEARCH METHODS

9.1 Study Design

The DUS of eliglustat will be undertaken in a series of prescription databases covering large populations to provide useful and reliable investigations of diseases as rare as Gaucher Disease. This DUS will be based on secondary use of data. This DUS is descriptive only with no comparative elements.

The study shall take the form of a cohort study using electronic health records. Gaucher Disease Type 1 patients identified in each prescription database who are being prescribed eliglustat will be followed from one year before their first prescription of eliglustat to the end of the study in Q3 2024. During this period, all prescriptions of past and CMI will be recorded (Appendix 1 in Section 14.1). The study will rely entirely on analysis of secondary data as described in the initial study synopsis submitted in the Risk Management Plan (RMP).

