9.4 Data Sources

This DUS is planned to take place in France, Denmark, Germany and Israel. Data sources of these countries accepted to participate but not all research agreements have been signed yet. In each of these countries, there are effective, population-based databases which provide a large coverage of the country. Also, national death registers are in place in all of these countries to ascertain the vital status of patients. Passive follow-up can be accomplished in all data sources thanks to a unique personal ID number which can be used to link together the information from several population-based registries.

Data from these databases will be used to identify GD1 patients treated with eliglustat. These databases cover a total population of approximately 100 million inhabitants.

These data sources can provide detailed data on eliglustat prescription and duration of use, and also on concomitant therapies listed in Appendix 1 in Section 14.1, provided that these drugs are marketed in the country.

In all data sources, data on the prescriber's specialty of eliglustat is available. However, there may be variability in the availability of these data, depending on decision of local competent authorities. In any event, the data from all data sources can address all DUS objectives. The data recorded in these data sources are considered to be valid for the information included in this study by the data holders.

Databases have been selected in European countries where eliglustat is approved and have been launched. Israel is considered as a European country since several agreements are in place between EU and Israel, including EMA agreements.

France

In France, the launching/reimbursement of eliglustat is effective since 09 November 2016.

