9.7.1 General Considerations

The exposure period for one patient corresponds to the period of eliglustat use. This period will be defined as the period between the exposure start date (the first record of eliglustat prescription) and the exposure end date (end of study or date of the last eliglustat prescription plus the duration of eliglustat use according to the last prescription or death date).

The statistical analyses will be only descriptive and will include the following:

• Descriptive analysis of eliglustat therapy in terms of duration and dose.

- Descriptive analysis of the past medication use (one year prior to the exposure period) in terms of proportion, therapeutic class and duration. The treatments of interest will be (details in Appendix 1 in Section 14.1):
 - Strong and moderate CYP2D6 inhibitors (CMI1 and CMI2)
 - Strong and moderate CYP3A inhibitors (CMI3 and CMI4)
 - Simultaneous use of strong or moderate CYP3A inhibitors with strong or moderate CYP2D6 inhibitors (CMI1 + CMI2 + CMI3 + CMI4)
 - Strong CYP3A inducers (CMI5)
 - P-gp substrates (CMI6)
 - CYP2D6 substrates (CMI7)

The proportions will be computed taking into account all treatments of interest and also by type of treatments and by duration. Proportions for the group CYP inhibitors will be also computed. The duration will be treated as a continuous variable and also as a categorical variable. The categorical variable will be defined as follow: 1. Total use will be defined as any prescription whatever the duration; 2. Chronic use will be defined as total duration of single or consecutive prescriptions of 15 days or over.

If the number of GD1 patients allows it, stratified analyses based on gender and age groups will be performed as well as analyses by year.

- Descriptive analysis of the concomitant medication use (i.e., during the exposure period) in terms of proportion, therapeutic class and duration. The treatments of interest will be the same as for the past medication use. The proportions will be computed as for the past medication use that is considering all treatments and also by therapeutic class and duration.
- Descriptive analysis of the health care service pattern (i.e., prescriber's specialty and types of patient visit) for the use of concomitant medications.

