	1.1.6 Final report of study results.	\square			6

¹ Date from which information on the first study is first recorded in the study dataset or, in the case of secondary use of data, the date from which data extraction starts.

² Date from which the analytical dataset is completely available.

Sect	ion 2: Research question	Yes	No	N/A	Section Number
2.1	Does the formulation of the research question and objectives clearly explain:	\boxtimes			
	2.1.1 Why the study is conducted? (e.g. to address an important public health concern, a risk identified in the risk management plan, an emerging safety issue)	\boxtimes			7.2
	2.1.2 The objective(s) of the study?	\square			8
	2.1.3 The target population? (i.e. population or subgroup to whom the study results are intended to be generalised)	\boxtimes			9.2.2
	2.1.4 Which hypothesis(-es) is (are) to be tested?			\boxtimes	
	2.1.5 If applicable, that there is no a priori hypothesis?			\square	

Comments:

Sect	Section 3: Study design		No	N/ A	Section Number
3.1	Is the study design described? (e.g. cohort, case- control, cross-sectional, other design)	\boxtimes			9.1
3.2	Does the protocol specify whether the study is based on primary, secondary or combined data collection?	\boxtimes			9.1
3.3	Does the protocol specify measures of occurrence? (e.g., rate, risk, prevalence)	\boxtimes			9.7
3.4	Does the protocol specify measure(s) of association? (e.g. risk, odds ratio, excess risk, rate ratio, hazard ratio, risk/rate difference, number needed to harm (NNH))	\boxtimes			9.7
3.5	Does the protocol describe the approach for the collection and reporting of adverse events/adverse reactions? (e.g. adverse events that will not be collected in case of primary data collection)				11.1

Sec	tion 4: Source and study populations	Yes	No	N/A	Section Number
4.1	Is the source population described?	\boxtimes			9.4
4.2	Is the planned study population defined in terms of:				

Section 4: Source and study population	s Yes	No	N/A	Section Number
4.2.1 Study time period	\square			9.2.1
4.2.2 Age and sex	\square			9.2.2
4.2.3 Country of origin	\square			9.2.4
4.2.4 Disease/indication				9.2
4.2.5 Duration of follow-up	\square			9.1
4.3 Does the protocol define how the stuc population will be sampled from the s population? (e.g. event or inclusion/exclusio	burce 🛛			9.2.2 9.2.3

Sect	ion 5: Exposure definition and measurement	Yes	No	N/ A	Section Number

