	9.1.2 Outcomes? (e.g. clinical records, laboratory markers or values, claims data, self-report, patient interview including scales and questionnaires, vital statistics)	\boxtimes			9.4
	9.1.3 Covariates and other characteristics?	\square			9.4
9.2	Does the protocol describe the information available from the data source(s) on:				
	9.2.1 Exposure? (e.g. date of dispensing, drug quantity, dose, number of days of supply prescription, daily dosage, prescriber)	\boxtimes			9.4

Sect	tion 9: Data sources	Yes	No	N/A	Section Number
	9.2.2 Outcomes? (e.g. date of occurrence, multiple event, severity measures related to event)	\square			9.4
	9.2.3 Covariates and other characteristics? (e.g. age, sex, clinical and drug use history, co-morbidity, co-medications, lifestyle)	\boxtimes			9.4
9.3	Is a coding system described for:				
	9.3.1 Exposure? (e.g. WHO Drug Dictionary, Anatomical Therapeutic Chemical (ATC) Classification System)	\boxtimes			9.3
	9.3.2 Outcomes? (e.g. International Classification of Diseases (ICD), Medical Dictionary for Regulatory Activities (MedDRA))	\boxtimes			9.3
	9.3.3 Covariates and other characteristics?	\square			9.3
9.4	Is a linkage method between data sources described? (e.g. based on a unique identifier or other)				9.4

Comments:

Section 10: Analysis plan	Yes	No	N/ A	Section Number
10.1 Are the statistical methods and the reason for their choice described?				9.7.1
10.2 Is study size and/or statistical precision estimated?		\boxtimes		9.5
10.3 Are descriptive analyses included?	\square			9.7
10.4 Are stratified analyses included?	\boxtimes			9.7
10.5 Does the plan describe methods for analytic control of confounding?			\boxtimes	
10.6 Does the plan describe methods for analytic control of outcome misclassification?			\boxtimes	
10.7 Does the plan describe methods for handling missing data?				9.8.1
10.8 Are relevant sensitivity analyses described?			\square	

Section 11: Data management and quality control	Yes	No	N/ A	Section Number
11.1 Does the protocol provide information on data storage? (e.g. software and IT environment, database maintenance and anti-fraud protection, archiving)	\boxtimes			9.6
11.2 Are methods of quality assurance described?	\boxtimes			9.8.1
11.3 Is there a system in place for independent review of study results?	\boxtimes			9.10.1

Section 12: Limitations	Yes	No	N/ A	Section Number
12.1 Does the protocol discuss the impact on the study results of:				
12.1.1 Selection bias?	\square			9.9

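### Sections 7.3 and 8 promise an assessment of risk-minimisation effectiveness, but the design is descriptive and ties no result to effectiveness; low co-use could not show that the measures worked

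*Protocol*

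**What the plan says.** The purpose is stated twice. Section 8 says "this DUS will allow to assess the effectiveness of risk minimisation measures (EU labelling, guide for prescribers and patient alert card", and extends this to both understanding and implementing the avoidance of interactions. Section 7.3 says "This DUS will allow to assess the effectiveness of risk minimisation measures that have been put in place and also to improve them".

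The design and analysis sections describe something narrower:

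- Section 9.1: "This DUS is descriptive only with no comparative elements".
- Section 9.7.1: "The statistical analyses will be only descriptive and will include the following".
- Section 8.1: "The primary objective of the DUS is to estimate the dose and duration of eliglustat therapy", together with past and concomitant medication use. Section 8.2 describes prescribers and visit types. Neither mentions effectiveness.
- Section 9.7.3.3: the same proportions and durations are computed separately for the year before the first delivery and for the whole period of eliglustat use.
- Sections 8.1 and 9.7.3.3: simultaneous use of a CYP2D6 and a CYP3A inhibitor is explored only if that proves feasible.
- Appendix 2: the item "Which hypothesis(-es) is (are) to be tested" is marked not applicable, and the item "Is study size and/or statistical precision estimated" is marked No.

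Section 9.4 adds that "Israel is considered as a European country since several agreements are in place between EU and Israel, including EMA agreements".

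**The concern.** A regulatory reader will take section 8 as the question the final report answers. An answer on effectiveness needs something to judge the observed co-use against: a comparison, a reference level or a criterion fixed beforehand. The protocol supplies none and section 9.1 excludes comparison. The likely consequence is a report that finds modest co-use and presents it as evidence that the label, prescriber guide and alert card work, which the design cannot support. Because the claim goes into a final report to the EMA, its wording decides what that report may conclude.

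**Working it through.** **1. Purpose against outputs.** For each element of the stated purpose, what does the protocol measure?

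- *Effectiveness:* no objective in 8.1 or 8.2 names it, and no section gives an acceptable level of co-use or a rule that turns a proportion into a judgement.
- *Understanding:* the data are prescription and dispensing records or medical charts (section 9.4). They show what was prescribed, not what prescribers or patients understood.
- *Avoidance of contraindicated combinations:* section 7.1 lists such combinations. The joint-inhibitor outcome is conditional on feasibility. The contraindication specific to CYP2D6 poor metabolisers needs the phenotype, and section 9.3.3 requires only age and sex, plus date of death.

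**2. Could the before/during proportions act as the comparison?** The first window is one year. The second is the whole exposure period, which section 9.7.3.2 expects to range from under one year to two years or more. With a constant yearly probability p of using a drug class, the proportion who ever use it in T years is 1 − (1 − p)^T. The values of p and the longer T are assumptions, since the protocol gives none.

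| p per year | T = 0.5 | T = 1 | T = 2 | T = 4 | T = 6 |
|---|---|---|---|---|---|
| 5% | 2.5% | 5% | 9.8% | 18.5% | 26.5% |
| 10% | 5.1% | 10% | 19.0% | 34.4% | 46.9% |
| 20% | 10.6% | 20% | 36.0% | 59.0% | 73.8% |

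At p = 10%, a one-year window gives 10% and a four-year window 34.4%, with no change in prescribing. Long users would seem to have increased co-use, and users of under a year to have reduced it. The raw difference therefore cannot be read as an effect of the measures, and section 9.7.3.3 does not define one.

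**3. Could the pilot act as a reference level?** Appendix 3 reports 10/48 = 20.8% with a CYP2D6 or a CYP3A inhibitor. The protocol does not adopt it as a benchmark. It concerns other Gaucher drugs, counts either inhibitor rather than both together, and includes sertraline, which is absent from Table 1 of Appendix 1.

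**4. What would the best possible result show?** The expected minimum in section 9.5 reproduces: 87 + 10 + 11 + 20 = 128. Section 9.7.1 has each source analysed separately. For zero events in n patients the exact (Clopper-Pearson) two-sided 95% upper limit is 1 − 0.025^(1/n):

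| Source | n | Upper limit with 0 events |
|---|---|---|
| France | 87 | 4.2% |
| Israel | 20 | 16.8% |
| Germany | 11 | 28.5% |
| Denmark | 10 | 30.8% |

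In three of the four sources, no observed co-use at all is compatible with true co-use of about one patient in six to nearly one in three.

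**The case against.** The best defence is that the effectiveness sentences are preamble. The formal objectives say estimate and describe, which agrees with 9.1 and 9.7.1, and no endpoint claims a test. Section 9.9 says results will be read in light of the limitations. A threshold could sit in the SAP or the risk management plan, neither of which is shown. This limits the damage but does not remove the conflict: the promise is made twice, one statement opens the research question, and a threshold elsewhere would not supply the comparison that 9.1 excludes or make understanding measurable.

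A second objection has real force. A reader might infer that no result could show that the measures worked or failed. The documents do not support that. Section 7.1 lists combinations that should not occur, so frequent use of them during eliglustat would be evidence of failure without any numeric target. The plan also reports past and concurrent use, country patterns and, if numbers allow, yearly trends. These are weak and tied to no verdict, but they exist. Nor can the plan be faulted for lacking eliglustat use without the label, since section 7.3 treats labelling as routine risk minimisation.

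Third, a reader might infer that Israel (20 of 128, 15.6%) should be excluded from any statement on EU measures. The protocol is silent on whether the label and materials applied there. Silence does not show that they did not, and results are reported by source.

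**Conclusion.** The point holds in a limited form. The protocol claims a property its design lacks: no comparison, reference level or criterion connects its outputs to effectiveness, and understanding cannot be observed in these data. The asymmetry matters. High use of contraindicated combinations could signal failure, whereas low use could not establish success. There is no counterfactual, and even zero events leaves upper limits of 4.2% to 30.8% by source.

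The limits assume the patient numbers expected in section 9.5 and separate analysis by source; larger cohorts would narrow them without supplying a comparison. The window figures are illustrative and assume constant yearly probabilities of 5% to 20%.

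A pass/fail threshold on the upper limit in each source might seem the natural remedy. It is not workable: with perfect prescribing, Israel, Germany and Denmark would still fail any tolerance below 16.8%, 28.5% and 30.8% respectively.

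**What to change.** Reword sections 7.3 and 8 to say that the study describes how often interacting drugs are prescribed with eliglustat while the risk minimisation measures are in place, and that this can signal failure of the measures but does not by itself establish their effectiveness. Remove the reference to understanding.

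If an effectiveness statement is kept:

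- name co-use of CYP2D6 and CYP3A inhibitors during eliglustat as the indicator before analysis, rather than leaving it conditional on feasibility;
- report it with exact 95% intervals for each source, as far as the small-cell rules in section 10.4 allow;
- make any before/during contrast in windows of equal length or per person-time;
- state whether the EU label and educational materials applied in Israel before including that source in a statement on EU measures.

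The rewording costs only protocol text and changes no data collection. The optional items add modest programming. The downside is a more modest claim to the regulator.
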